1726 overall type 1 error for the primary outcome plus seven key secondary outcomes identified above.

1727 All Other Secondary Analyses

1728 For all above-mentioned secondary analyses, the false discovery rate will be controlled using the
1729 adaptive Benjamini-Hochberg procedure.

1730 **11.16 Exploratory Analyses**

1731 In addition to the analysis for the CGM-measured endpoints described earlier, separate analyses
1732 will be conducted for daytime and nighttime.

1733 The CGM-measured analyses will be replicated with only CGM data when the closed-loop was
1734 active for the CLC group. The CGM data for the SC group will be the same as mentioned above
1735 in the CGM Metrics Calculation section 11.4.3.

1736

Chapter 12: Data Collection and Monitoring

1737 **12.1 Case Report Forms and Device Data**

1738 The main study data are collected through a combination of electronic case report forms
1739 (CRFs) and electronic device data files obtained from the study software and individual hardware
1740 components. These electronic device files and electronic CRFs from the study website are
1741 considered the primary source documentation.

1742 When data are directly collected in electronic case report forms, this will be considered the source
1743 data. Each participating clinical center will maintain appropriate medical and research records for
1744 this trial, in compliance with ICH E6 and regulatory and institutional requirements for the
1745 protection of confidentiality of participants.

1746 **12.2 Study Records Retention**

1747 Study documents should be retained for a minimum of 2 years after the last approval of a marketing
1748 application in an ICH region and until there are no pending or contemplated marketing applications
1749 in an ICH region or until at least 2 years have elapsed since the formal discontinuation of clinical
1750 development of the investigational product. These documents should be retained for a longer
1751 period, however, if required by local regulations. No records will be destroyed without the written
1752 consent of the sponsor, if applicable. It is the responsibility of the sponsor to inform the
1753 investigator when these documents no longer need to be retained.

1754 **12.3 Quality Assurance and Monitoring**

1755 Designated personnel from the Coordinating Center will be responsible for maintaining quality
1756 assurance (QA) and quality control (QC) systems to ensure that the clinical portion of the trial is
1757 conducted and data are generated, documented and reported in compliance with the protocol, Good
1758 Clinical Practice (GCP) and the applicable regulatory requirements. Adverse events will be
1759 prioritized for monitoring.

1760 A risk-based monitoring (RBM) plan will be developed and revised as needed during the course
1761 of the study, consistent with the FDA “Guidance for Industry Oversight of Clinical Investigations
1762 — A Risk-Based Approach to Monitoring” (August 2013). Study conduct and monitoring will
1763 conform with 21 Code of Federal Regulations (CFR) 812.

1764 The data of most importance for monitoring at the clinical center are participant eligibility and
1765 adverse events. Therefore, the RBM plan will focus on these areas. As much as possible, remote
1766 monitoring will be performed in real-time with on-site monitoring performed to evaluate the verity
1767 and completeness of the key clinical center data. Elements of the RBM may include:

- 1768 • Qualification assessment, training, and certification for clinical centers and clinical center
1769 personnel
- 1770 • Oversight of Institutional Review Board (IRB) coverage and informed consent procedures
- 1771 • Central (remote) data monitoring: validation of data entry, data edits/audit trail, protocol

1772 review of entered data and edits, statistical monitoring, study closeout

1773 • On-site monitoring (site visits): source data verification, site visit report

1774 • Agent/Device accountability

1775 • Communications with clinical center staff

1776 • Participant retention and visit completion

1777 • Quality control reports

1778 • Management of noncompliance

1779 • Documenting monitoring activities

1780 • Adverse event reporting and monitoring

1781 Coordinating Center representatives or their designees may visit the study facilities at any time
1782 in order to maintain current and personal knowledge of the study through review of the records,
1783 comparison with source documents, observation and discussion of the conduct and progress of the
1784 study.

1785 **12.4 Protocol Deviations**

1786 A protocol deviation is any noncompliance with the clinical trial protocol, GCP, or procedure
1787 requirements. The noncompliance may be either on the part of the participant, the investigator, or
1788 the clinical center staff. As a result of deviations, corrective actions are to be developed by the
1789 clinical center and implemented promptly.

1790 The clinical center PI/study staff is responsible for knowing and adhering to the IRB requirements.
1791 Further details about the handling of protocol deviations will be included in the monitoring plan.

1792

Chapter 13: Ethics/Protection of Human Participants

1793 **13.1 Ethical Standard**

1794 The investigator will ensure that this study is conducted in full conformity with Regulations for
1795 the Protection of Human Participants of Research codified in 45 CFR Part 46, 21 CFR Part 50, 21
1796 CFR Part 56, and/or the ICH E6.

1797 **13.2 Institutional Review Boards**

1798 The protocol, informed consent form(s), recruitment materials, and all participant materials will
1799 be submitted to the IRB for review and approval. Approval of both the protocol and the consent
1800 form must be obtained before any participant is enrolled. Any amendment to the protocol will
1801 require review and approval by the IRB before the changes are implemented to the study. All
1802 changes to the consent form will be IRB approved; a determination will be made regarding whether
1803 previously consented participants need to be re-consented.

1804 **13.3 Informed Consent Process**

1805 **13.3.1 Consent Procedures and Documentation**

1806 Informed consent is a process that is initiated prior to the individual's agreeing to participate in the
1807 study and continues throughout the individual's study participation. Extensive discussion of risks
1808 and possible benefits of participation will be provided to the participants and their families.
1809 Consent forms will be IRB-approved and the participant will be asked to read and review the
1810 document. The investigator will explain the research study to the participant and answer any
1811 questions that may arise. All participants will receive a verbal explanation in terms suited to their
1812 comprehension of the purposes, procedures, and potential risks of the study and of their rights as
1813 research participants. Participants will have the opportunity to carefully review the written consent
1814 form and ask questions prior to signing.

1815 The participants should have the opportunity to discuss the study with their surrogates or think
1816 about it prior to agreeing to participate. The participant will sign the informed consent and child
1817 assent documents prior to any procedures being done specifically for the study. The participants
1818 may withdraw consent at any time throughout the course of the trial. A copy of the informed
1819 consent and child assent documents will be given to the participants for their records. The rights
1820 and welfare of the participants will be protected by emphasizing to them that the quality of their
1821 medical care will not be adversely affected if they decline to participate in this study.

1822 **13.3.2 Participant and Data Confidentiality**

1823 The study monitor, other authorized representatives of the sponsor, representatives of the IRB or
1824 device company supplying study product may inspect all documents and records required to be
1825 maintained by the investigator, including but not limited to, medical records (office, clinic, or
1826 hospital) for the participants in this study. The clinical center will permit access to such records.

1827 The study participant's contact information will be securely stored at each clinical center for
1828 internal use during the study. At the end of the study, all records will continue to be kept in a
1829 secure location for as long a period as dictated by local IRB and Institutional regulations.

1830 Study participant research data, which is for purposes of statistical analysis and scientific reporting,
1831 will be transmitted to and stored at the Jaeb Center for Health Research and the University of
1832 Virginia Center for Diabetes Technology. This will not include the participant's contact or
1833 identifying information. Rather, individual participants and their research data will be identified
1834 by a unique study identification number. The study data entry and study management systems
1835 used by clinical centers and by Jaeb research staff will be secured and password protected. At the
1836 end of the study, all study databases will be de-identified and archived at Jaeb Center for Health
1837 Research and the University of Virginia Center for Diabetes Technology. Permission to transmit
1838 data will be included in the informed consent.

Chapter 14: References

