- 1221 • evaluation or treatment was obtained at a health care provider facility for an acute event
1222 involving hyperglycemia or ketosis
- 1223 • blood ketone level ≥ 1.5 mmol/L and communication occurred with a health care provider at
1224 the time of the event
- 1225 • blood ketone level ≥ 3.0 mmol/L, even if there was no communication with a health care
1226 provider

1227 Hyperglycemic events are classified as DKA if the following are present:

1228 • Symptoms such as polyuria, polydipsia, nausea, or vomiting;

1229 • Serum ketones ≥ 1.5 mmol/L or large/moderate urine ketones;

1230 • Either arterial blood pH < 7.30 or venous pH < 7.24 or serum bicarbonate < 15 ; and

1231 • Treatment provided in a health care facility

1232 All reportable Adverse Events—whether volunteered by the participant, discovered by study
1233 personnel during questioning, or detected through physical examination, laboratory test, or other
1234 means—will be reported on an adverse event form online. Each adverse event form is reviewed
1235 by the Medical Monitor to verify the coding and the reporting that is required.

1236 **9.1.3 Relationship of Adverse Event to Study Device**

1237 The study investigator will assess the relationship of any adverse event to be related or unrelated
1238 by determining if there is a reasonable possibility that the adverse event may have been caused by
1239 the study device.

1240 To ensure consistency of adverse event causality assessments, investigators should apply the
1241 following general guideline when determining whether an adverse event is related:

1242 Yes

1243 There is a plausible temporal relationship between the onset of the adverse event and the study
1244 intervention, and the adverse event cannot be readily explained by the participant's clinical state,
1245 intercurrent illness, or concomitant therapies; and/or the adverse event follows a known pattern of
1246 response to the study intervention; and/or the adverse event abates or resolves upon discontinuation
1247 of the study intervention or dose reduction and, if applicable, reappears upon re-challenge.

1248 No

1249 Evidence exists that the adverse event has an etiology other than the study intervention (e.g.,
1250 preexisting medical condition, underlying disease, intercurrent illness, or concomitant
1251 medication); and/or the adverse event has no plausible temporal relationship to study intervention.

1252 **9.1.4 Intensity of Adverse Event**

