1253 The intensity of an adverse event will be rated on a three point scale: (1) mild, (2) moderate, or (3)
1254 severe. It is emphasized that the term severe is a measure of intensity: thus, a severe adverse event
1255 is not necessarily serious. For example, itching for several days may be rated as severe, but may
1256 not be clinically serious.

1257 • **MILD:** Usually transient, requires no special treatment, and does not interfere with the
1258 participant's daily activities.

1259 • **MODERATE:** Usually causes a low level of inconvenience or concern to the participant and
1260 may interfere with daily activities, but is usually ameliorated by simple therapeutic measures.

1261 • SEVERE: Interrupts a participant's usual daily activities and generally requires systemic drug
1262 therapy or other treatment.

1263 **9.1.5 Coding of Adverse Events**

1264 Adverse events will be coded using the MedDRA dictionary. The Medical Monitor will review
1265 the investigator's assessment of causality and may agree or disagree. Both the investigator's and
1266 Medical Monitor's assessments will be recorded. The Medical Monitor will have the final say in
1267 determining the causality.

1268 Adverse events that continue after the participant's discontinuation or completion of the study will
1269 be followed until their medical outcome is determined or until no further change in the condition
1270 is expected.

1271 **9.1.6 Outcome of Adverse Event**

1272 The outcome of each reportable adverse event will be classified by the investigator as follows:

- 1273 • RECOVERED/RESOLVED – The participant recovered from the AE/SAE without sequelae.
1274 Record the AE/SAE stop date.

- 1275 • RECOVERED/RESOLVED WITH SEQUELAE – The event persisted and had stabilized
1276 without change in the event anticipated. Record the AE/SAE stop date.

- 1277 • FATAL – A fatal outcome is defined as the SAE that resulted in death. Only the event that
1278 was the cause of death should be reported as fatal. AEs/SAEs that were ongoing at the time of
1279 death; however, were not the cause of death, will be recorded as “resolved” at the time of death.

- 1280 • NOT RECOVERED/NOT RESOLVED (ONGOING) – An ongoing AE/SAE is defined as the
1281 event was ongoing with an undetermined outcome.

- 1282 ○ An ongoing outcome will require follow-up by the clinical center in order to determine the
1283 final outcome of the AE/SAE.

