1315 If pregnancy occurs, the participant will be discontinued from the study. The occurrence of
1316 pregnancy will be reported on an AE Form.

1317 **9.4 Timing of Event Reporting**

1318 SAEs and UADEs must be reported to the Coordinating Center within 24 hours via completion of
1319 the online serious adverse event form.

1320 Other reportable adverse events, device malfunctions (with or without an adverse event), and
1321 device complaints should be reported promptly by completion of an electronic case report form,
1322 but there is no formal required reporting period.

1323 The Coordinating Center will notify all participating investigators of any adverse event that is
1324 serious, related, and unexpected. Notification will be made within 10 days after the Coordinating
1325 Center becomes aware of the event.

1326 Each principal investigator is responsible for reporting serious study-related adverse events and
1327 abiding by any other reporting requirements specific to his/her Institutional Review Board or
1328 Ethics Committee.

1329 Upon receipt of a UADE report, the Sponsor will investigate the UADE and if indicated, report
1330 the results of the investigation to the clinical centers' IRBs, and the FDA within 10 working days
1331 of the Sponsor becoming aware of the UADE per 21CFR 812.46(b). The Medical Monitor must
1332 determine if the UADE presents an unreasonable risk to participants. If so, the Medical Monitor
1333 must ensure that all investigations, or parts of investigations presenting that risk, are terminated as

1334 soon as possible but no later than 5 working days after the Medical Monitor makes this
1335 determination and no later than 15 working days after first receipt notice of the UADE.

1336 In the case of a device system component malfunction (e.g. pump, CGM, control algorithm),
1337 information will be forwarded to the responsible company by the clinical center personnel, to be
1338 handled by its complaint management system.

1339 **9.5 Stopping Criteria**

1340 **9.5.1 Participant Discontinuation of Study Device**

1341 Rules for discontinuing study device use are described below.

1342 • The investigator believes it is unsafe for the participant to continue on the intervention. This
1343 could be due to the development of a new medical condition or worsening of an existing
1344 condition; or participant behavior contrary to the indications for use of the device that imposes
1345 on the participant's safety

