1346 • The participant requests that the treatment be stopped

1347 • Participant pregnancy

1348 • Two distinct episodes of DKA

1349 • Two distinct severe hypoglycemia events as defined in section 9.1.2.1

1350 If pregnancy occurs, the participant will be discontinued from the study entirely. Otherwise, even
1351 if the study device system is discontinued, the participant will be encouraged to remain in the study
1352 through the final study visit.

1353 **9.5.2 Criteria for Suspending or Stopping Overall Study**

1354 In the case of an unanticipated system malfunction resulting in a severe hypoglycemia or severe
1355 hyperglycemia event (as defined in section 9.1.2.2), use of the study device system will be
1356 suspended while the problem is diagnosed.

1357 In addition, study activities could be similarly suspended if the manufacturer of any constituent
1358 study device requires stoppage of device use for safety reasons (e.g. product recall). The affected
1359 study activities may resume if the underlying problem can be corrected by a protocol or system
1360 modification that will not invalidate the results obtained prior to suspension. The study Medical
1361 Monitor will review all adverse events and adverse device events that are reported during the study
1362 and will review compiled safety data at periodic intervals (generally timed to the review of
1363 compiled safety data by the DSMB). The Medical Monitor may request suspension of study
1364 activities or stoppage of the study if deemed necessary based on the totality of safety data available.

1365 **9.6 Independent Safety Oversight**

1366 A Data and Safety Monitoring Board (DSMB) will review compiled safety data at periodic
1367 intervals (typically every 6 months). In addition, the DSMB will review all DKA and severe
1368 hypoglycemia irrespective of relatedness to study device use, and all serious events (including
1369 UADEs) related to study device use at the time of occurrence. The DSMB also will be informed
1370 of any ADEs not meeting criteria for a UADE if the Medical Monitor requests the DSMB

1371 review. The DSMB can request modifications to the study protocol or suspension or outright
1372 stoppage of the study if deemed necessary based on the totality of safety data available. Details
1373 regarding DSMB review will be documented in a separate DSMB document.

1374 **9.7 Risks**

1375 The potential risks associated with use of the study device are described in section 1.3.

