341 criteria mentioned above for the primary outcome. The event rates per week will be compared using
342 similar linear mixed effects regression models as described above for the primary outcome.

343 The following will be summarized and tabulated by treatment group:

- 344 • Other serious adverse events (SAE)
- 345 • BG-measured hypoglycemic events (days with at least one BG record < 54 mg/dL)
- 346 • BG-measured hyperglycemic events (days with at least one BG record > 350 mg/dL)
- 347 • Worsening of HbA1c from baseline to 16 weeks by $> 0.5\%$
- 348 • Related to Investigational Device Usage (intervention group only):
 - 349 ○ Adverse device effects (ADE)
 - 350 ○ Serious adverse device events (SADE)

351 ○ Unanticipated adverse device effects (UADE)

352 **8. Intervention Adherence**

353 *Closed Loop System*

354 The amount of closed loop system use for the CLC group will be calculated from downloaded data over
355 the period from the day after randomization until the day before the 16 week visit. Any dropouts will be
356 counted as zero use for the remainder of the study.

357 Percent time in different operation modes overall and by 4-week periods will be tabulated and boxplots
358 will be created by 4-week periods.

359 *CGM Use*

360 The amount of CGM sensor use for both treatment groups will be calculated from downloaded data in
361 the same way as closed-loop system use described above.

362 Percent time sensor use overall and by 4-week periods will be tabulated by treatment group and boxplots
363 will be created by 4-week periods.

364 *Blood Glucose Monitoring*

365 Average daily frequency of downloaded BGM use for both treatment groups will be calculated similarly
366 in the same time window. If a participant drops out of the study or no meter download is available for a
367 specific period, average daily BGM use will be set to missing for that period.

368 The average daily frequency of downloaded BGM use overall and by 4-week periods will be tabulated
369 by treatment group.

370 **9. Protocol Adherence and Retention**

371 The following tabulations and analyses will be performed by treatment group to assess protocol
372 adherence for the study:

373 • Number of protocol and procedural deviations
374 • Flow chart accounting for all enrolled participants up to randomization
375 • Flow chart of all randomized participants at all scheduled visits and phone contacts post
376 treatment initiation

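### For serious events other than DKA and severe hypoglycemia, the Medical Monitor's causality rating alone can take an event the investigator called device-related out of immediate DSMB review and investigator notification

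*Protocol*

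**What the plan says.** Protocol 9.1.3 asks the investigator to rate each adverse event as related or unrelated to the study device. Protocol 9.1.5 then has the Medical Monitor review "the investigator's assessment of causality and may agree or disagree. Both the investigator's and" the Medical Monitor's ratings are kept. The section closes with the deciding rule: "The Medical Monitor will have the final say in" determining causality. At the end of 9.1.2.2, each adverse event form is reviewed "by the Medical Monitor to verify the coding and the reporting that is required".

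Relatedness is then used in three places.

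- **Protocol 9.6, DSMB review as events occur.** The sentence has two limbs. The first is unconditional: "In addition, the DSMB will review all DKA and severe" "hypoglycemia irrespective of relatedness to study device use, and all serious events (including" UADEs begins the second limb, which covers other serious events only when they are "related to study device use at the time of occurrence".
- **Protocol 9.4, notice to all investigators.** This applies to any event that is "serious, related, and unexpected. Notification will be made within 10 days after the Coordinating" Center learns of it.
- **SAP section 7, device tables.** Under the label "Related to Investigational Device Usage (intervention group only" the SAP lists adverse device effects (ADE), serious adverse device events (SADE) and unanticipated adverse device effects (UADE). Protocol 11.8 has the same list. Neither document names the assessor whose rating is used.

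Protocol 9.6 also says that the DSMB hears of ADEs short of a UADE if the Medical Monitor asks for that review. Periodic DSMB review of compiled data is typically six-monthly.

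**The concern.** Two people rate causality, and the plan keeps both answers. It then lets one answer decide whether the independent board and the other centers are told promptly. Where the investigator who saw the child says related and the Medical Monitor says unrelated, the disputed event follows the slower route. Disputed events are among those on which the board's own early view is most useful.

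The prompt look matters more here because Protocol 11.13 and SAP section 12 give the DSMB no formal stopping rules beyond the participant-level and study-level criteria in Protocol 9.5. Much of the oversight therefore rests on review of individual events. Protocol 1.2 and 11.13 also say that the data may support a PMA application, so it should be clear how the device-related counts were formed.

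**Working it through.** No figure in either document bears on this point. The check is to trace what changes, and what does not, when a serious event rated related by the investigator is re-rated unrelated by the Medical Monitor.

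| Pathway | Where | Depends on relatedness? |
|---|---|---|
| Immediate DSMB review of DKA and severe hypoglycemia | Protocol 9.6 | No |
| Immediate DSMB review of other serious events | Protocol 9.6 | Yes |
| Notice to all investigators within 10 days | Protocol 9.4 | Yes (also serious and unexpected) |
| ADE/SADE/UADE tables | Protocol 11.8, SAP 7 | Yes, assessor not named |
| SAE report to the Coordinating Center within 24 hours | Protocol 9.4 | No |
| Periodic DSMB review of compiled data | Protocol 9.6 | No filter stated |
| Other-SAE table by group | Protocol 11.8, SAP 7 | No |
| Any-adverse-event rate | Protocol 11.8, SAP 7 | No |

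**Step 1: which rating decides.** Protocol 9.1.5 answers this directly. Neither document has an adjudication step or a rule that either rating suffices, and nothing keeps the investigator's rating in force for 9.4 or 9.6. The guideline for judging relatedness in 9.1.3 is addressed to investigators. No criterion is given for overturning a related rating.

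**Step 2: which events are exposed.** DKA and severe hypoglycemia are not. Other serious events are. One example lies within the protocol's own definitions: a child admitted to hospital with ketosis who does not meet the pH or bicarbonate criterion for DKA in 9.1.2.2. The admission makes it an SAE under 9.1.1, it is not DKA, and whether the DSMB sees it at the time depends on relatedness.

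**Step 3: what the delay could be.** Six months is 6 × 52/12 = 26 weeks. The randomized phase is 16 weeks, and with the 12-week extension a participant's time after randomization is 16 + 12 = 28 weeks. An event that waits for the next periodic review could wait anything from almost no time to about 26 weeks. The upper end is longer than the whole randomized phase for that participant. It also reaches into the period in which standard-care participants move to the device.

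**Step 4: the tables.** If the final determination feeds SAP section 7, the re-rated event also leaves the device-related rows. That is an inference from 9.1.5, because the SAP does not say so.

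**Step 5: non-serious events.** An ADE short of a UADE reaches the DSMB between periodic reviews only at the Medical Monitor's request. Under 9.1.2 some non-serious events are reportable only because they are ADEs. The documents do not say whether such an event stays in the any-adverse-event rate once it is rated unrelated.

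**The case against.** The strongest reply is that the plan has several safeguards that do not pass through this rating.

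- The two events singled out for formal comparison and for participant stopping, DKA and severe hypoglycemia, go to the DSMB whatever their cause.
- Every SAE reaches the Coordinating Center within 24 hours.
- Principal investigators keep their own duty to report to their IRBs.
- A UADE report triggers a sponsor investigation on receipt.
- Device malfunctions are reported and tabulated separately, with listed exceptions.

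All of this stands, and it limits the point to the events in step 2. It does not put a disputed event of that kind before the board promptly, and IRB reporting by one site does not alert the others.

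A second reply is that central review applies one standard across up to four centers and can also raise a rating from unrelated to related. That is a good reason to keep the Medical Monitor's rating. It is not a reason to let it cancel the investigator's for routing.

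A third reply is that Protocol 9.6 leaves details of DSMB review to a separate document, and that 9.6 and 9.4 do not say whether forwarding waits for the Medical Monitor's ruling. Both are true, which is why the conclusion is that the event *can* leave these routes, not that it will. The unseen document may add a route, but it does not change the rule as 9.1.5 states it.

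A reader might go further and infer that one person can remove an event from the trial's safety record. The documents do not support that. Both ratings are kept, and the SAE stays in the 24-hour reports, the compiled DSMB data, the SAE table and the any-adverse-event rate. It is reclassified, not deleted.

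**Conclusion.** The point holds for serious events other than DKA and severe hypoglycemia. For these, a change from related to unrelated by the Medical Monitor can take the event out of immediate DSMB review and all-investigator notification, leaving the board to see it at a periodic review that is typically six-monthly. An effect on the ADE/SADE/UADE tables is possible but not established, because SAP section 7 names no assessor.

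The size can be described only in kind. The documents give no expected number of such events and no rate of disagreement, so any probability that an event is delayed, or any percentage by which device-related counts fall, would only restate assumed inputs. It would also be wrong to infer that immediate DSMB review as a whole depends on relatedness, since 9.6 exempts the two most prominent event types.

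The conclusion assumes that *related* in 9.4 and 9.6 means the final determination under 9.1.5, which is the natural reading. The primary analysis is not affected. This is an inexpensive improvement in safety oversight that should be made.

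**What to change.** - **Protocol 9.1.5, 9.4 and 9.6:** state that an event is routed as device-related, for immediate DSMB review and for notice to investigators, if either the investigator or the Medical Monitor rates it related. The other conditions in 9.4 and 9.6 stay as they are. The Medical Monitor's rating is still recorded and can accompany the notice.
- **SAP section 7:** name the assessor whose rating feeds the ADE, SADE and UADE tables, and report the number of events on which the two ratings differ.

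Both ratings are already collected, so no new data are needed. The cost is a wording change and a few more notices to the DSMB and investigators.
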